10.9 Confidentiality of Data

Subject medical information obtained by this study is confidential, and disclosure to third parties other than those noted below is prohibited.

With the subject's permission, medical information may be given to his or her personal physician or other appropriate medical personnel responsible for his or her welfare.

Data generated by this study must be available for inspection by representatives of the USA FDA, national and local health authorities, the Sponsor or their designee, and the IRB/EC.

10.10 Retention of Records

USA FDA regulations (21 CFR 312.62[c]) require that records and documents pertaining to the conduct of this study and the distribution of investigational drug, including CRFs, consent forms, laboratory test results, and medical inventory records, must be retained by the Principal Investigator for 2 years after marketing application approval. If no application is filed, these records must be kept 2 years after the investigation is discontinued and the USA FDA and the applicable national and local health authorities are notified. The Sponsor or their designee will notify the Principal Investigator of these events.

10.11 Protocol Adherence

Each Investigator must adhere to the protocol as detailed in this document and agrees that any changes to the protocol must be approved by the Sponsor or their designee prior to seeking approval from the IRB. Each Investigator will be responsible for enrolling only those subjects who have met protocol eligibility criteria.

11. PUBLICATION PLAN

The study will be listed in the ClinicalTrials.gov registry. Study results will be made public and disseminated to individual research sites in a timely manner, and no later than one year after study completion.

13. APPENDICES

13.1 Appendix 1: Clinical Laboratory Tests

Clinical Chemistry	Hematology	Urinalysis
Total Bilirubin	Hemoglobin	pН
AST (SGOT)	Hematocrit	Color
ALT (SGPT)	Erythrocytes	Transparency
BUN	Leukocytes + differential	Specific Gravity
Glucose	Thrombocytes (platelet count)	Urobilinogen
Potassium		Ketones
Sodium		Protein
Calcium		Glucose
Alkaline Phosphatase		Hemoglobin
Chloride		
Creatinine		
CO ₂		

ALT = alanine transferase; AST = aspartate transferase; BUN = blood urea nitrogen

13.2 Appendix 2: Schedule of Events – 26 Week Treatment Period

WEEK		0	2	4	8	17	26	
VISIT	V1 Screen ing	V2 Base line	V3 +/- 3 days	V4 +/- 3 days	V5 +/- 3 days	V6 +/- 7 days	V7 Final Visit ⁴ +/- 7 days	Unscheduled Visit or Dose Escalation Visit ⁶
			Screening &	& Diagnosis				
Informed consent	X							
Demographics	X							
Medical History	X	X						
Retrospective Seizure Diary Collection and Review	X							
Inclusion/Exclusion criteria	Х	X						
Background AEDs Review	X	X	X	X	X	X	X	X
Concomitant Med Review	X	X	X	X	X	X	X	X
			Safety As	sessments				
ECG	X			X				
Vital Signs ⁵	X	X	X	X	X	X	X	X
Physical Examination ¹	X	X	X	X	X	X	X	X
Neurological Examination ¹	X	X	X	X	X	X	X	X
Safety Labs (Blood ⁷ and Urine ²)		X			X		X	X
Urine Pregnancy Test (WCBP)		X		X	X	X	X	
Administer C-SSRS		X	X	X	X	X	X	X
EEG		X		X	X	X	X	
Review safety and record AEs			X	X	X	X	X	X
			Efficacy A	ssessments				
Instruct/ Provide Seizure Calendar	X	X	X	X	X	X	X	X
Subject Calendar Review	X	X	X	X	X	X	X	X
Complete CGII-C			_	X	X	X	X	
Instruct and Collect CGII-P				X	X	X	X	

Page 52 08 April 2016

WEEK		0	2	4	8	17	26	
VISIT	V1 Screen ing	V2 Base line	V3 +/- 3 days	V4 +/- 3 days	V5 +/- 3 days	V6 +/- 7 days	V7 Final Visit ⁴ +/- 7 days	Unscheduled Visit or Dose Escalation Visit ⁶
			Other A	ssessment	s			
VAS		X			X		X	
PK/PD Assessments								
Concomitant AED medications		X			X		X	
Study Drug Blood Samples					X		X	
Neurosteroid levels		X			X		X	
Study Medication								
Dispense Medication		X	X ³	X ³				
Collect bottles from prior visit study medication			X	X	X	X	X	X
Instruct on Down-titration							X ⁸	

- 1. Physical and neurological exam records performed at the same center within 60 days of screening visit may be used in place of screening exam. Visits 3, 4, 5 and 6 may be follow-up exams. Tanner Scores will be collected.
- 2. Obtain urine sample for those who are toilet trained.
- 3. Adjust dose if necessary.
- 4. This visit could also be an Early Termination visit. At this visit, investigator confirms if the subject qualifies for the 52 week extension, subjects must have completed all scheduled clinical study visits and have shown a minimum 35% improvement in mean seizure frequency per 28 days vs. baseline.
- 5. Vital signs including temperature, blood pressure, pulse, height and weight.
- 6. A dose escalation visit is required 4-6 days after escalation to any dose level above 54 mg/kg/day or above 1500 mg/day. A regularly scheduled visit may serve as a dose escalation visit. An unscheduled visit can occur at any time during the 26 week open-label treatment period or the 52 week extension. Samples for concomitant AEDs and study drug levels may also be drawn if warranted in the opinion of the investigator.
- 7. Safety labs can be collected at any visit if warranted in the opinion of the investigator.
- 8. If this is the last study visit, the subject should be instructed on down-titration and scheduled for Visit 11 which is the follow-up visit.

AEs = adverse events; AED = antiepileptic drug; ECG = electrocardiogram; C-SSR=Columbia Suicide Severity Rating; EEG= Electroencephalography; VAS=Visual Analogue Scale

Schedule of Events - 52 Week Open-Label Extension

WEEK	44	62	78	
VISIT	V8	V9	V10 ⁴	V11
	+/- 14	+/- 14	+/- 14	Follow-
	days	days	days	up +/- 7
				days
Screening & Diagnosis				,
Background AEDs Review	X	X	X	X
Concomitant Med Review	X	X	X	X
Safety Assessments				
Vital Signs ⁵	X	X	X	X
Physical Examination	X	X	X	
Neurological Examination	X	X	X	
Safety Labs (Blood ⁷ and Urine ²)	X	X	X	
Urine Pregnancy Test (WCBP)	X	X	X	
Administer C-SSRS	X	X	X	X
Review safety and record AEs	X	X	X	X
Efficacy Assessments				
Instruct/ Provide Seizure Calendar	X	X	X	
Subject Calendar Review	X	X	X	X
EEG	X	X	X	
Complete CGII-C	X	X	X	
Instruct and Collect CGII-P	X	X	X	
Other Assessments				
VAS		X	X	
PK/PD Assessments				
Concomitant AED medications	X	X	X	
Study Drug Blood Samples	X	X	X	
Neurosteroid levels	X	X	X	
Study Medication				
Dispense Medication	X ³	X ³	X ³	

Collect bottles from prior visit study medication	X	X	X	X
Instruct on Down-titration			X8	

- 1. Physical and neurological exam records performed at the same center within 60 days of screening visit may be used in place of screening exam. Visits 3, 4, 5 and 6 may be follow-up exams. Tanner Scores will be collected.
- 2. Obtain urine sample for those who are toilet trained.
- 3. Adjust dose if necessary.
- 4. This visit could also be an Early Termination visit. At this visit, investigator confirms if the subject qualifies for the 52 week extension, subjects must have completed all scheduled clinical study visits and have shown a minimum 35% improvement in mean seizure frequency per 28 days vs. baseline.
- 5. Vital signs including temperature, blood pressure, pulse, height and weight.
- 6. A dose escalation visit is required 4-6 days after escalation to any dose level above 54 mg/kg/day or above 1500 mg/day. A regularly scheduled visit may serve as a dose escalation visit. An unscheduled visit can occur at any time during the 26 week open-label treatment period or the 52 week extension. Samples for concomitant AEDs and study drug levels may also be drawn if warranted in the opinion of the investigator.
- 7. Safety labs can be collected at any visit if warranted in the opinion of the investigator.
- 8. If this is the last study visit, the subject should be instructed on down-titration and scheduled for Visit 11 which is the follow-up visit.

AEs = adverse events; AED = antiepileptic drug; ECG = electrocardiogram; C-SSR=Columbia Suicide Severity Rating; EEG= Electroencephalography

13.3 Appendix 3: Strong and Moderate Cytochrome P450 CYP 3A4, 5, 7 Inducers and Inhibitors Prohibited During Study 1042-0900

Prohibited Strong and	Prohibited Strong and Moderate
Moderate CYP 3A4 Inhibitors	CYP 3A4 Inducers*
amprenavir	avasimibe
aprepitant	bosentan
atazanavir	efavirenz
boceprevir	etravirine
ciprofloxacin	modafinil
clarithromycin	nafcillin
conivaptan	rifabutin
diltiazem	rifampin
erythromycin	St. John's wort
fluconazole	troglitazone (not sold in US, Russia)
fluvoxamine	
fosamprenavir	
grapefruit juice	
imatinib	
indinavir	
itraconazole	
ketoconazole	
mibefradil (not sold in US)	
nefazodone (not sold in US)	
nelfinavir	
Group aconazole	
ritonavir	
saquinavir	
telaprevir	
telithromycin	
troleandomycin (not sold in US,	
Russia)	
verapamil	
voriconazole	

^{*}Carbamazepine and phenytoin are both moderate CYP 3A4 inducers but are permitted as background AEDs during the study.

Data from

 $\frac{http://www.fda.gov/Drugs/DevelopmentApprovalProcess/DevelopmentResources/DrugInteractionsLabeling/ucm080499.htm}{nsLabeling/ucm080499.htm} \ and \ http://medicine.iupui.edu/clinpharm/ddis/ClinicalTable.aspx; access$

13.5 Appendix 5: Protocol History

Revision #	Date	Revisions					
V0:	November 25, 2014						
V1:	December 10, 2014	Minor edits and clarifications.					
V2:	January	Minor edits and clarifications.					
	12, 2015	pgs. 25, 26 and 42					
		For consistency with Section 9.5.4 Other Assessment and the Synopsis , a statement was added regarding the blood collection to measure allopregnanolone, and related neurosteroids in the Visit 2 and Visit 4 Schedule of Study Procedures section and Schedule of Events.					
V3:	January	Dosing regimen revised for subjects: p 3, 15, 19-20.					
	23, 2015	A visit at Week 2 and procedures for unscheduled visits have been added: p. 4, 24, 26, 29, and Appendix 2.					
		Collection of blood for Liver Function Test and other laboratory assessments have been added at the Week 26 visit: p. 4, 28, 31 and Appendix 2.					
		Guidance on missed doses for the capsules and suspension has been clarified: p. 18.					
V4:	June 8, 2015	Collection of EEG's have been added on Visits 2, 5 and 7. See Synopsis, p.23, 25, 27, 28 and Appendix 2.					
V5:	July 15,	See Appendix 5.1 for complete summary of changes.					
	2015	Addition of CDKL5 and Dravet Syndrome Subjects:					
		Background has been updated.					
		Seizure criteria has been updated for the CDKL5 and Dravet Syndrome subjects.					
		Contraindicated medications for Dravet patients have been added.					
		Male children are also eligible for inclusion.					
		• Age has been increased from 2-10 years to 2-18 years age.					
		 Pregnancy Testing has been added for WCBP. 					
		o Tanner Scale score has been added under Physical Exam					

	Ι	
		52 week extension for subjects who respond to ganaxolone:
		Criteria for inclusion has been added.
		3 additional visits have been added.
		Study Assessments Added:
		Additional study drug PK samples and concomitant AED samples to be drawn at existing blood draw at Week 26.
		Administrative Changes:
		Study Title has been updated.
		Sponsor Contact information has been updated.
		Clarifying statements that the screening and baseline visit can be combined.
V5.1	September 30, 2015	Local Amendment – (Site #006)
	30, 2013	 Stiripentol has been added as an Exclusion Criteria in section 9.3.3 and to the list in Appendix 3 of "Prohibited Strong and Moderate CYP 3A4 Inhibitors"
1		

V 6.0	April 2016	Local Amendment (Site #001)
		See Appendix 6 for Summary of Changes
		 Inclusion of other genetic epilepsies. These include, but are not limited to children with PCDH19 mutation, CDKL5 Disorder, Dravet Syndrome and other epileptic syndromes such as LGS, CSWS, and other potential genetic or clinical conditions with or without corresponding genetic condition (referred as genetic epilepsies) in an open-label proof-of-concept study.
		Inclusion of additional EEG assessments
		• Addition of the Visual Analogue Scale (VAS-Targeted Behavior) at baseline, Visits 5, Visit 7, Visit 9 and Visit 10.
		• Stiripentol (Italy specific) has been added as an Exclusion Criteria in section 9.3.3
		• Stiripentol (not sold in the US) has been added to the list in Appendix 3 of "Prohibited Strong and Moderate CYP 3A4 Inhibitors"
		• Visual Analogue Scale (VAS-Target Behavior) has been added to Appendix 7

13.6 Appendix 6: Amendment #5.2 Summary of Changes

There is one major revision to this protocol.

Addition of LGS, CSWS, encephalopathic epilepsy and other potential genetic epilepsies subjects. Despite trying multiple AEDs, many of these patients still do not have adequate seizure control. Since ganaxolone does have a unique mechanism of action and the safety and efficacy of ganaxolone has been well studied, it is reasonable to believe that ganaxolone could be beneficial to these subjects as well.

A number of sections have been revised to accommodate the addition of these epilepsies. In addition, administrative information has been updated. The revisions to the updated sections are described below:

Section 9.3.2 Inclusion Criteria

#3 Revised to include LGS, CSWS, or other genetic epilepsies and reads as follows:

"In the opinion of the investigator have confirmed PCH19 genetic mutation, confirmed CDKL5 genetic mutation or Dravet Syndrome confirmed by a SCN1A mutation, or genetic epilepsy testing confirming a LSG or CSWS condition associated with this genetic phenotype. Refractive cases of LGS or CSWS that remain idiopathic or have prior history of steroid or ACTH response can also be entered if documentation confirms specific genetic defects are not found and prior steroid response clinically occurred"

#4 Revised to include seizure criteria relevant for LGS, CSW and other genetic epilepsies and reads as follows:

- a. "Have uncontrolled cluster seizures (3 or more seizures over the course of 12 hours) every 6 weeks or less during baseline, or bouts of status epilepticus on intermittent basis, or"
- b. No revisions made
- c. No revisions made
- d. Have subclinical CSWS syndrome with or without clinical events on EEG

Section 9.3.3 Exclusion Criteria

#6 Revised to include stiripentol as an exclusionary medication for subjects with Dravet Syndrome enrolled in Italy and reads as follows:

For Dravet Syndrome subjects the following are also excluded: phenytoin, fosphenytoin, carbamazepine, oxcarbazepine, lamotrigine, rufinamide and stiripentol (Italy specific).

#6 Revised to include criteria for the use of cannabadiol and epidolex for LGS, CSWS or other genetic epilepsies per standard practice and reads as follows:

"Patients on cannabadiol (CBD) products that have shown <75 improvement must be withdrawn from CBD and be off product >28 days before Visit 2"
"Patients on CBD products that have shown >75% improvement and have completed or discontinued from the blinded clinical study, are on maintenance CBD for >6 months or taking epidolex with stable laboratory values and no SAEs will, on a case by case basis, be considered for enrollment. The decision to taper or leave the patient on the drug before adding ganaxolone will be made, if it is believes to be unethical to take the patient off drug and promote status epilepticus or loss of gained >75% improvement of seizure control. The patient will need to meet criteria for current entry seizure frequency for the ganaxolone study."

#10 Revised to include conditions for subjects who are on a ketogenic diet and reads as follows:

"Are planning to follow a ketogenic diet. If on ketogenic diet more than 6 months with stable laboratory values and seizure control then enrollment will be made on a case by case basis"

Section 9.5.5 Schedule of Study Procedures and Appendix 2 Schedule of Events

EEG added to Visit 4, Visit 6, Visit 8, Visit 9 and Visit 10

Visual Analogue Scale (VAS-Target Behavior) added at baseline, Visit 5, Visit 7, Visit 9 and Visit 10

Section 13.7 Appendix 7

Section 13.7.4 Visual Analogue Scale (VAS-Target Behavior) added

Administrative Change

Sponsor Contact information has been updated

13.7 Appendix 7: Seizure Calendar & Ratings

- 13.7.1: Clinical Global Impression of Improvement: Clinician & Clinical Global Impression of Improvement: Patient/Caregiver
- 13.7.2: Columbia-Suicide Severity Rating Scale Baseline & Visit
- 13.7.3: Subject Seizure Calendar & Investigator Instructions
- 13.7.4: Visual Analogue Scale (VAS-Targeted Behavior)

13.7.1 Clinical Global Impression of Improvement: Clinician & Clinical Global Impression of Improvement: Patient/Caregiver

Clinical Global Impression–Improvement (CGI-I) - Clinician

Circle the appropriate response that adequately describes how the subject's symptoms have improved or worsened relative to baseline before the beginning of the study (ie. before study drug was taken).

1=very much improved

2= much improved

3= minimally improved

4= no change

5= minimally worse

6= much worse

7= very much worse

Clinical Global Impression-Improvement (CGI-I) - Patient/Caregiver

Circle the appropriate response that adequately describes how your (or your child's) symptoms have improved or worsened relative to baseline before the beginning of the study (ie. before study drug was taken).

- 1=very much improved
- 2= much improved
- 3= minimally improved
- 4= no change
- 5= minimally worse
- 6= much worse
- 7= very much worse

13.7.2 Columbia Suicide Severity Scale: Baseline/Screening (Version 6/23/10) Columbia Suicide Severity Scale: Children's Since Last Visit (Version 6/23/10) 13.7.3 Seizure Calendar and Investigator Instructions

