9.5.5.2 Visit 2 (Baseline; Week 0)

- Review medical history, background AEDs and other concomitant medications
- Review inclusion/exclusion criteria
- Collect and review seizure calendars
- VAS
- Administer Columbia Suicide Scale assessed for children 7 years and older
- Perform physical and neurological examinations
- Measure vital signs
- Draw blood sample for, hematology, chemistry, trough concomitant AED levels, and allopregnanolone, and related endogenous CNS-active steroids; obtain urine sample from subjects who are toilet trained for urinalysis and pregnancy test for WCBP.
- Dispense study medication and dosing instructions
- Instruct and provide study Subject Seizure Calendar
- EEG

- Screening and Baseline visits may be one visit if the seizure calendar data are sufficient.
- 9.5.5.3 Visit 3 (end of Week 2 + / 3 days)
 - Review background AEDs and other concomitant medications
 - Collect and review seizure calendars; provide new calendars
 - Administer Columbia Suicide Scale assessed for children 7 years and older
 - Perform follow-up physical and neurological examinations
 - Assess for adverse events
 - Measure vital signs
 - Collect bottles from prior visit study medication
 - Adjust dose if necessary
 - Dispense study medication
- 9.5.5.4 Visit 4 (end of Week 4 +/- 3 days)
 - Review background AEDs and other concomitant medications
 - Collect and review seizure calendars; provide new calendars
 - Complete CGII-Clinician Ratings
 - Instruct and collect CGII-Patient/Caregiver Ratings
 - Administer Columbia Suicide Scale assessed for children 7 years and older
 - Perform follow-up physical and neurological examinations
 - Assess for adverse events
 - Measure vital signs
 - 12-lead ECG
 - EEG
 - Collect bottles from prior visit study medication
 - Adjust dose if necessary
 - Dispense study medication
 - Urine Pregnancy Test for WCBP

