9.5.5.5 Visit 5 (end of Week 8 +/-3 days)

- Review background AEDs and other concomitant medications
- Collect and review seizure calendars; provide new calendars
- Complete CGII-Clinician Ratings
- Collect CGII-Patient/Caregiver Ratings
- VAS
- Administer Columbia Suicide Scale assessed for children 7 years and older
- Perform follow-up physical and neurological examinations
- Assess for adverse events
- Measure vital signs
- EEG
- Draw blood sample for hematology, chemistry, trough study drug, concomitant AED levels, and allopregnanolone, related endogenous CNS-active steroids; obtain urine sample from subjects who are toilet trained for urinalysis and pregnancy test for WCBP.
- Collect bottles from prior visit study medication
- Adjust dose if necessary & Dispense study medication

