9.5.5.12 Dose Escalation Visit and Unscheduled Visits

- Review background AEDs and other concomitant medications
- Collect and review seizure calendars; provide new calendars
- Administer Columbia Suicide Scale assessed for children 7 years and older
- Perform follow-up physical and neurological examinations
- Assess for adverse events
- Measure vital signs
- Draw blood sample for hematology, chemistry; obtain urine sample from subjects who are toilet trained for urinalysis and pregnancy test for WCBP.
- Collect bottles from prior visit study medication
- Adjust dose if necessary
- Dispense study medication

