2.3 TIME WINDOWS FOR ANALYSIS

For by visit safety or efficacy summaries, only scheduled visits will be analyzed.

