7.3.5 C-SSRS

The C-SSRS data will be summarized and listed for each question by visit.

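### C-SSRS tables use scheduled visits only, so a positive answer on a Since Last Visit form from an unscheduled visit can be missing from every C-SSRS summary; unequal look-backs also make the by-visit shares hard to compare

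*Protocol*

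**What the plan says.** Protocol Appendix 7 (13.7.2) names two C-SSRS forms, one for baseline or screening and one for later visits: "Columbia Suicide Severity Scale: Children's Since Last Visit (Version 6/23/10"). Protocol 9.5.5 places the scale at every visit from baseline onward: "Visit 2 (Baseline; Week 0"), "Visit 3 (end of Week 2"), "Visit 4 (end of Week 4 +/- 3 days"), "Visit 5 (end of Week 8 +/-3 days"), then Weeks 17, 26, 44, 62, 78 and 82. The SAP's schedules (Tables 1 and 2) give the same weeks through 78.

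The scale is also given outside that calendar. Protocol 9.5.5.12, on dose-escalation and unscheduled visits, reads: "Administer Columbia Suicide Scale assessed for children 7 years and older". Protocol 9.4.4 requires a visit 4 to 6 days after each escalation above 1500 mg/day, or above 54 mg/kg/day for children of 30 kg or less.

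The whole analysis plan for the scale is SAP 7.3.5: "The C-SSRS data will be summarized and listed for each question by visit." SAP 2.3 adds: "For by visit safety or efficacy summaries, only scheduled visits will be analyzed." SAP 7 sends assessments at unscheduled time points to the listings. SAP 2.1 gives the 26-week period and the extension separate tables.

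**The concern.** A since-last-visit form restarts its look-back each time it is completed. An extra form between two scheduled visits takes over part of the interval that the next scheduled form would have covered. If the extra form is then kept out of the tables, that part of the interval is summarised nowhere for the C-SSRS. Required post-escalation visits are one source of such forms, so the gap can fall just after the highest doses.

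A second issue concerns reading the by-visit table. When the look-back differs between columns, the share positive for new events differs even at constant risk. A longer window could be mistaken for an effect of longer exposure.

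The C-SSRS is a named safety endpoint (SAP 1.2.3), safety and tolerability are the secondary objective, and the SAP states that no DSMB was used. By-visit tables also cannot show how many different children were ever positive.

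**Working it through.** The documents give no C-SSRS rate, so there is no planned figure to reproduce. The calendar does check: 12 + 26 + 52 + 4 = 94 weeks, the stated maximum participation.

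**Part 1: forms missing from the tables (no rate assumed).**

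- The form is given at dose-escalation and unscheduled visits (Protocol 9.5.5.12; same column in Appendix 2 and SAP Table 1).
- By-visit summaries use scheduled visits only (SAP 2.3), and the by-visit summary is the only C-SSRS summary (SAP 7.3.5).
- Hence an answer on such a form enters no C-SSRS summary unless the visit coincides with a scheduled one.
- Neither document carries an unscheduled answer forward to the next scheduled visit.

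Examples of the interval left out:

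- Extra form at Week 5: the Week 8 form covers 3 of 4 weeks; 1/4 = 25% of the window is untabulated.
- Extra form at Week 40: the Week 44 form covers 4 of 18 weeks; 14/18 = 78% is untabulated.

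In the suggested schedule for 30 kg (Appendix 4), two steps (55 and 60 mg/kg; 1650 and 1800 mg) lie above the threshold that triggers an extra visit.

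**Part 2: unequal look-back.** Window = difference between consecutive scheduled weeks. Expected share = 1 − exp(−rate × window), for new events at a constant rate. The 0.5% per week is an assumption.

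| Visit | Week | Window (weeks) | Share at 0.5%/week | Ratio to Visit 3 |
|---|---|---|---|---|
| 3 | 2 | 2 | 1.00% | 1.0 |
| 4 | 4 | 2 | 1.00% | 1.0 |
| 5 | 8 | 4 | 1.98% | 2.0 |
| 6 | 17 | 9 | 4.40% | 4.4 |
| 7 | 26 | 9 | 4.40% | 4.4 |
| 8 | 44 | 18 | 8.61% | 8.65 |
| 9 | 62 | 18 | 8.61% | 8.65 |
| 10 | 78 | 16 | 7.69% | 7.7 |
| 11 (post-drug) | 82 | 4 | 1.98% | 2.0 |

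For example, Visit 8 is 1 − exp(−0.09) = 8.61% and Visit 3 is 1 − exp(−0.01) = 0.995%; 8.61/0.995 = 8.65.

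Sensitivity to the assumed rate:

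- From 0.02 to 0.20 events per child per 26 weeks, the ratio to Visit 3 is 4.49 down to 4.38 at Visit 7, and 8.94 down to 8.47 at Visits 8 and 9.
- At 2% per week, Visit 3 is 3.9% and Visit 8 is 30.2%, a ratio of 7.7.

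The ratios therefore depend little on the rate; the absolute shares depend on it heavily.

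Visit tolerances widen the windows: Visit 3 covers 11 to 17 days, Visit 8 covers 105 to 147 and Visit 9 covers 98 to 154.

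As a check that the window causes the pattern, take 0.10 per 26 weeks and divide each share by window length. The result is 1.49% to 1.53% per 4 weeks at every visit, against 0.77% to 6.69% unadjusted.

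**The case against.** Several points on the other side are sound.

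- **Nothing is lost from the report as a whole.** Unscheduled forms stay in the listings (SAP 7). A clinically significant finding can be recorded as an adverse event, and SAP 7.1 tabulates those by start date. A reader might infer that positive answers after escalation vanish from every summary; the documents do not support that. The gap is in the C-SSRS tables. The adverse-event route does not close it, because it depends on an event being recorded and does not count children by C-SSRS item.
- **Some post-escalation forms are tabulated.** A regular visit may serve as the escalation visit (footnote 6 to the schedules). Protocol 9.4.4 also speaks of scheduling the escalation visit, so its exclusion under SAP 2.3 is a reading. It is the natural one, because both schedules put dose-escalation and unscheduled visits in one column apart from the numbered visits.
- **A steady rise with time on drug is not built in.** A reader might infer this from the 2-week and 18-week windows. But windows are equal at Visits 3 and 4, 6 and 7, and 8 and 9, and shorten at Visits 10 and 11. The main and extension tables are separate, so the contrast of nearly 9-fold appears in no single table. Extension entry also requires completed visits and at least 35% improvement, so the two sets of children differ. Persistent ideation does not scale with window length, and if still present it would show again on the next scheduled form.
- **Counts will be very small.** Only children aged 7 and older are assessed, and each cohort was planned at up to 10. Even with all 10 assessed, 0.5% per week gives 10 × 1.00% = 0.1 expected positives at Visit 3 and 10 × 8.61% = 0.9 at Visit 8. The look-back artefact would be hard to see. Small counts weigh the other way for Part 1: one omitted child is a material share of a cohort.
- **Version.** The form is named only in the supplied protocol, dated April 2016, and its items are not shown. The SAP cites Amendment 8.1 of August 2017. If that amendment changed the form, the point would need rechecking.

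**Conclusion.** The point holds as a gap in the planned C-SSRS summaries. Under SAP 7.3.5 and 2.3, a positive answer on a form from a visit that is not a scheduled one reaches no C-SSRS summary table, and the next scheduled form no longer covers that interval. A table could show zero while a listing holds a positive. This follows from the stated rules and the form's name, with no assumed rate. It matters most for events that resolve before the next scheduled visit.

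The unequal look-back is secondary. Its size, about 4.4-fold within the main table and 8.7-fold across the two tables, rests on a constant rate of new events. The documents supply no rate, and the SAP plans no test across visits. It is a reason to label the columns, not evidence that the table would show a false trend.

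**What to change.** In SAP 7.3.5, add one summary table for each period (26-week and extension), by cohort and overall: the number and percent of assessed children with any post-baseline suicidal ideation or behaviour, using all forms, scheduled or unscheduled. The denominator should be children with at least one post-baseline form in that period. State that SAP 2.3 does not restrict this table.

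Keep the by-visit table, with a footnote giving the nominal look-back at each visit, and show the actual look-back in days in the listing. A rate per patient-year is optional; it would need a defined countable event and would add little at these numbers.

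The cost is SAP wording, one added table, a footnote and a listing column. All the data are already collected.
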